5.3 SCREENING FOR ELIGIBILITY

Patients will be screened daily, based on the inclusion/exclusion criteria as specified in the protocol by the local ICU research team and/or members of the usual care team (where they are appropriately trained).

A screening log will form part of the eCRF and be maintained by sites. This will include no personal information but will collect data on reasons for non-enrolment to enable reporting according to the CONSORT Guidelines for parallel group randomised clinical trials.

5.4 INELIGIBLE AND NON-RECRUITED PARTICIPANTS

Ineligible and non-recruited patients will continue to receive usual care as directed by the clinical care team.

5.5 RANDOMISATION

5.5.1 Randomisation Procedures

Randomisation will be performed by a member of the research team at each site using an automated web-based system developed by the ECTU, using variable block sizes and stratified by centre, ensuring allocation concealment. Participants will be randomised at 1:1 allocation ratio to either Usual Care alone or Dexamethasone plus Usual Care intervention. This is an open-label trial where patients, clinicians and assessors are aware of the treatment assignment post randomisation.

5.5.2 Treatment Allocation

Participants randomised to the intervention arm will be administered dexamethasone intravenously within four hours post randomisation and then daily for the next 9 days or until the time they discharged from critical care setting (ICU/HDU) to a general ward (whichever is

sooner). Participants will start on a dose of Dexamethasone base 16.5mg (equivalent to Dexamethasone Phosphate 20mg) and will then be administered 16.5mg dexamethasone base from the next calendar day after 10am and once a day up to day 5 post randomisation. From day 6 participants will be administered Dexamethasone base 8.25mg (equivalent to Dexamethasone Phosphate 10mg) per day for up to 10 days post randomisation (i.e., 5 further days - days 6, 7, 8, 9 and 10) or until the patient is discharged from ICU/HDU. Participants randomised to the usual care arm will receive the usual care as per local clinical practice and will provide follow-up data as a comparator.

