6.3 DOSING REGIME

Each participant randomised to the intervention arm will be administered Dexamethasone base 16.5mg (equivalent to Dexamethasone Phosphate 20mg) on days 1 to 5 followed by Dexamethasone base 8.25mg (equivalent to Dexamethasone Phosphate 10mg intravenously once a day on days 6 to 10. The daily doses will be administered once a day at approximately the same time each day.

Dexamethasone solution for injection can be given without mixing or dilution. When dexamethasone solution for injection is given by intravenous infusion, glucose 5% in water and sodium chloride 0.9% have been recommended as diluents, as per site practice. Critical Care nurses with appropriate training will prepare and administer dexamethasone as per standard site practice. No weaning off the dexamethasone dose is required after the 10 days treatment period.

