6.6 OVERDOSE

As the maximum daily dose is 16.5mg (as base) and is administered by appropriate clinical staff, who are trained and experienced in administering medicinal products, overdose is extremely unlikely. Reports of acute toxicity and/or deaths following overdosage with glucocorticoids are rare. No antidote is available so in the case of an overdose symptomatic treatment should be administered as per local policy.

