7.4 LONG TERM FOLLOW UP ASSESSMENTS

Long term follow-ups will be checked at site. The primary objective of mortality will be checked at 60d post randomisation. At this time the HRQol will be measured using EQ-5D. Patients will be asked to complete a HRQol questionnaire at 60, 90 and 180 days post randomisation. These questionnaires will be completed in person, via phone or email. Long-term follow up data on health care use will be obtained with data linkage as described in Section-8. A health resource use questionnaire will be carried out by a phone call with the patient at 60, 90 and 180 days by a member of the research team.

Table 3: Schedule of events

Events and Procedures	Screen ing (Day 0)	Randomisat ion (Day 1)	Day 2-5	Day 6-10	ICU Stay	In hospital stay	Day 60	Day 90	Day 180
Study Procedures									
Informed consent	Х								
Medical History	Х								
Review and confirm eligibility	X								
Demographics	X								
Baseline data	X								
Research blood		Х ^а	\mathbf{X}^{b}						
samples		^	^						
Intervention									
Usual Care or									
Dexamethasone		Х	Х	X					
Treatment									
Efficacy Measures									
First successful					Х	X			
extubation									
Mechanical Ventilation		х	Х	Χ	Х				
status									
Organ support		X	Х	Х	Х				
information									
AE/SAE Recording		Х	Χ	Χ					
Duration of stay					Х	Х			
Long Term Follow-up									
HRQoL							Χ	Х	Χ
Mortality							Χ	Х	Χ
Health Resource Use							X	Х	Χ

^a Prior to first dose of the intervention

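### When randomisation and first dose straddle midnight, or the first dose falls well before 10am, Sections 5.5.2, 6.3, 6.6 and Table 3 do not give one consistent dexamethasone schedule

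*Protocol*

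**What the plan says.** All references are to the protocol.

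- **Section 5.5.2, first dose.** Dexamethasone is given "within four hours post randomisation and then daily for the next 9 days", or until discharge from critical care if that is sooner.
- **Section 5.5.2, later doses.** After the 16.5 mg starting dose (as base), participants "will then be administered 16.5mg dexamethasone base from the next calendar day after 10am and once a day up to day 5 post randomisation". The 8.25 mg level then covers "5 further days - days 6, 7, 8, 9 and 10".
- **Section 6.3.** The 16.5 mg level is given "on days 1 to 5 followed by Dexamethasone base 8.25mg" on days 6 to 10. It adds: "The daily doses will be administered once a day at approximately the same time each day". Section 6.4 holds this regimen fixed while the patient is in ICU or HDU.
- **Section 6.1.1.** Prescribing is described as five days at each level.
- **Section 6.6.** Part of the argument that overdose is very unlikely is "As the maximum daily dose is 16.5mg (as base").
- **Table 3 (Section 7.4).** Randomisation is Day 1, with treatment marked on that day; screening is Day 0.
- **Section 6.5.** The time of each dose goes into the trial database.

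The protocol does not say what the next calendar day follows, which day number a first dose after midnight takes, whether the same-time rule includes the first dose, or whether the daily maximum refers to a date or to 24 hours.

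**The concern.** The first dose is set by elapsed time and the second by date and clock. The two systems agree while randomisation and first dose fall on the same date and the first dose is not in the early morning. Outside that range the sections give different instructions to the same bedside nurse.

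For the affected patients, dose spacing, dose on a single date and possibly total dose depend on which section the site follows. One reading exceeds the daily maximum that the protocol itself states. The same dosing record could also be compliant under one section and a deviation under another, which bears on the deviation log and violation reports of Section 14.2. A statistical analysis plan cannot settle a bedside instruction, so the protocol has to.

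**Working it through.** **The plan's own count.** One first dose plus nine further days = 10 doses = 5 + 5. Total base dose = 5 × 16.5 + 5 × 8.25 = 82.5 + 41.25 = 123.75 mg. Sections 5.5.2, 6.1.1 and 6.3 agree on this.

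**Case 1: first dose before midnight.** Randomised 22:00, dosed 23:30. The 10am rule sets a floor and no ceiling, so the second dose can be given at 23:30 next day: a 24-hour gap, one dose per date, 5 + 5 doses on Days 1 to 10. No conflict.

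**Case 2: randomisation and first dose straddle midnight.** Randomised 22:30 (Day 1), dosed 01:30 (Day 2 on Table 3's numbering), inside the four-hour limit.

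- *Next day counted from randomisation.* The second dose is due after 10:00 on the same date as the first, from 8.5 hours later. Dose on that date = 2 × 16.5 = 33 mg, twice the 16.5 mg in Section 6.6 and contrary to once-daily dosing. The 5 + 5 count is kept. The shortest gap arises with randomisation at 23:59 and first dose at 03:59: 03:59 to 10:00 is about 6 hours.
- *Next day counted from the first dose.* The second dose is due after 10:00 on Day 3, at least 32.5 hours later. Day 1 has no dose. If the site changes level after the day labelled 5 and stops after the day labelled 10, the doses at 16.5 mg fall on Days 2 to 5 only: 4 × 16.5 + 5 × 8.25 = 66 + 41.25 = 107.25 mg. The shortfall is 16.5 / 123.75 = 13%.

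**Case 3: randomisation and first dose both after midnight on one date, before 10am.** There is one dose per date, 10 doses, and never more than 16.5 mg on a date. Only the clock time is in question, because the second dose may not precede 10:00 next day:

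| First dose | Smallest gap to second dose | Smallest shift in clock time |
|---|---|---|
| 02:00 | 32 h | 8 h |
| 05:00 | 29 h | 5 h |
| 08:00 | 26 h | 2 h |
| 09:30 | 24.5 h | 0.5 h |

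The conflict with Section 6.3 is clear in the small hours and vanishes towards 10:00. A first dose that has crossed midnight meets the same shift if the second dose is counted from it.

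**How many patients.** The protocol gives no distribution of randomisation or dosing times. Purely for illustration, assume randomisation uniform over 24 hours and delay to first dose uniform over 0 to 4 hours. The share straddling midnight is (4/24) × 1/2 = 8.3%; of about 854 in the dexamethasone arm that is 854 × 0.083 ≈ 71. A grid in 15-minute steps gives the same: 136 of 1632 combinations. On that grid, Case 3 first doses that miss the same-time rule make up 29%, 25% or 17% for an assumed tolerance of 1, 2 or 4 hours (476, 408 or 272 of 1632).

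**The case against.** The best defence is that the text, read sensibly, already resolves most of this. In Section 5.5.2 the nearest event before the next-day rule is the starting dose, and the same sentence requires one dose a day, so the reading that yields 33 mg works against its own sentence. Section 6.6 describes why overdose is unlikely; it is not written as a dosing limit and does not define a day. The 4 + 5 count requires a site to put Table 3's labels above the explicit count of nine further days and five days at each level. Section 6.3 can be read as governing only the daily doses that follow the first. Four hours is an upper limit, so a site can usually dose before midnight.

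Much of this stands. It makes the same-time conflict the weaker limb and the lost dose conditional. It does not remove the problem. Counting the first dose as the anchor still leaves Day 1 of Table 3 empty and makes the labels that follow randomisation disagree with the dose count. Numbering Day 1 from the first dose would restore the count but departs from Table 3. Nothing tells sites to dose before midnight, while Section 5.2.2 wants treatment started as soon as possible after eligibility is established.

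A reader might infer more: that every patient first dosed overnight is caught, that a site is forced to double or drop a dose, or that compliance cannot be assessed. The documents do not support that. Case 1 meets every rule, a double or lost dose arises only in Case 2 and only under particular readings, and Section 6.5 captures dose times and reasons for missed doses for everyone.

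**Conclusion.** The inconsistency is real and limited to a minority of intervention patients. If randomisation and first dose straddle midnight, one reading gives 33 mg on one date with a gap as short as about 6 hours; the other leaves Day 1 undosed and, with day labels taken literally, gives 107.25 mg instead of 123.75 mg. If the first dose falls between midnight and well before 10am, the 10am floor conflicts with the same-time rule unless that rule excludes the first dose.

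The 33 mg result assumes that the next day is counted from randomisation and that the daily maximum refers to a date. The 107.25 mg result assumes Table 3's labels override the stated dose counts. The 8% figure rests wholly on uniform times and counts midnight crossings, not dosing errors.

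This is a minor to moderate clarification of dosing instructions. It deserves action because it touches patient safety and the protocol's own stated maximum. It has no effect on sample size, alpha or power, and the intention-to-treat primary analysis is unchanged.

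**What to change.** Reconcile Sections 5.5.2, 6.3 and 6.6 with Table 3 so that they state:

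1. which event the next calendar day is counted from;
2. which day number a first dose given after midnight takes;
3. whether the same-time rule in Section 6.3 includes the first dose, given the 10am floor in Section 5.5.2.

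Use the same numbering in the eCRF dose form, so that compliance is judged against one schedule. Which rule stands is for the sponsor to decide.

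The cost is a wording amendment and an adjustment to the eCRF dose form, with no extra patients or procedures.

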5.5.3 Emergency Unblinding Procedures

GuARDS will be an open label trial, emergency unblinding procedures are not applicable.

5.6 WITHDRAWAL OF STUDY PARTICIPANTS

Participants are free to withdraw from the study at any point. If such a withdrawal occurs, the primary reason for withdrawal will be documented in the participant's case record form. Data collected up to the point of withdrawal will be retained by the study team. The participant will have the option of withdrawal from:

- (i) **Study medication only** where continued study follow-up and collection of data by linkage permitted.
- (ii) Study medication and follow up but data linkage permitted.
- (iii) All aspects of the trial but continued use of data collected up to that point.
- (iv) Information already collected to be used in future ethically approved research studies.

To safeguard rights, the minimum personally identifiable information possible will be collected.

Randomised participants who wish to be withdrawn from the study before they have undertaken any study related procedures will be withdrawn from the study and another participant will be recruited to replace them. Data on the original participant will be kept on the CRF/database if the participant agrees to this.

The site PI can also withdraw a participant, based on clinical reasons, often made in patient's best interests. In this scenario, the main reasons for withdrawal will need to be documented in the eCRF.

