4.1 NUMBER OF PARTICIPANTS

A maximum of 1708 participants will be randomised 1:1 dexamethasone plus standard care vs, standard of care alone (around 854 per group).

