10.2 PROPOSED ANALYSES

As highlighted in Section-3 GuARDS Trial is a parallel group, allocation concealed, open label, pragmatic, group sequential design randomised controlled trial⁴⁴, with internal pilot, with frequentist analyses.

One experimental treatment (intravenous dexamethasone) is compared with usual care (control) arm. Prior to the first formal interim analysis, we will generate a detailed Statistical Analysis Plan (SAP), which will include details of how missing data will be accounted for in the analyses.

Analyses will be two-sided and tested at an a priori significance level of p=0.05. The primary analyses will be conducted on an intention-to-treat basis, with all randomised patients being analysed in the group to which they were allocated, regardless of the subsequent treatment they received. Results will be reported in accordance with Consolidated Standards of Reporting Trials guidance for parallel group clinical trials⁴⁶.

We will describe baseline characteristics, follow-up measurements and safety data, using suitable measures of central tendencies; means and medians with the associated standard deviations and interquartile ranges for continuous data; and frequencies and proportions for categorical data (including binary data).

The primary outcome for the randomised groups will be analysed using a logistic regression model, adjusted for age, and severity of hypoxaemia at baseline as two pre-defined baseline prognostic covariates. Analysis of secondary outcomes will involve fitting models appropriate to the type of outcome measure (i.e. time-to-event, binary, continuous).

Subgroup analyses will be provided on the primary outcome, for baseline patients features age category (≤65 years vs. >65 years), sex, comorbidities (number, and diabetes status), shock status, pneumonia diagnosis, baseline illness severity, and ARDS features (pulmonary

vs extra pulmonary, sepsis status, baseline mechanical ventilation status, severity of hypoxaemia, and extent of chest radiology involvement). These analyses will be based on an intention-to-treat population and will be restricted to participants with non-missing subgroup data at baseline.

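### Section 5.6 replaces randomised participants who withdraw before any study procedure, which does not fit the intention-to-treat rule, the cap of 1708 randomised, or its own data-retention sentence

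*Protocol*

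**What the plan says.** Four statements in the Protocol bear on this.

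- **Section 5.6, replacement.** The rule covers "Randomised participants who wish to be withdrawn from the study before they have undertaken any study related procedures". Such people "will be withdrawn from the study and another participant will be recruited to replace them". The next sentence adds: "Data on the original participant will be kept on the CRF/database if the participant agrees to this".
- **Section 5.6, opening paragraph.** For withdrawals in general: "Data collected up to the point of withdrawal will be retained by the study team". No agreement is required there.
- **Section 10.2.** The primary analysis is by intention to treat, "with all randomised patients being analysed in the group to which they were allocated, regardless of the subsequent treatment they received".
- **Section 4.1.** "A maximum of 1708 participants will be randomised 1:1".

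Three further facts give the context. Section 5.5.1 states that patients, clinicians and assessors all know the allocation once randomisation has happened. Section 5.5.2 allows up to four hours between randomisation and the first dose. Section 10.1.3 derives 1656 patients with complete outcomes and raises this to 1708 for an expected loss of less than 3% at 60 days.

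**The concern.** Replacing a randomised person suggests that the newcomer takes that person's place in the trial. Under intention to treat nobody's place can be taken: once randomised, a person belongs to the denominator of the allocated arm. If a site or analyst acts on section 5.6 in its ordinary sense, some randomised people may drop out of the primary analysis set, or may leave no retained record from which to count them.

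The rule operates only after allocation is known, so the decision to leave can depend on the arm. If it also depends on prognosis, the people left in the two arms are no longer comparable on 60-day mortality. Data that were never retained cannot be restored at analysis, so the matter has to be settled in the protocol.

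**Working it through.** **1. The plan's own sample size.** Inputs from sections 10.1.1 to 10.1.3: control mortality 0.40, absolute reduction 0.08 (so 0.32 on dexamethasone), two-sided alpha 0.05, power 0.90, no continuity correction.

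Fixed-sample size per arm = [1.960 × √(2 × 0.36 × 0.64) + 1.2816 × √(0.40 × 0.60 + 0.32 × 0.68)]² / 0.08² = 755, or 1510 in total. The stated 1656 implies a group-sequential inflation of 1656 / 1510 = 1.097. Numerical integration of the stated boundaries at 50%, 65%, 80% and 100% information gives a one-sided alpha of 0.0250 with futility ignored. With 1656 patients and futility followed, power is 0.899 (pooled variance) or 0.901 (unpooled). Then 1656 / 0.97 = 1707.2, rounded up to 1708. The stated figures reproduce, so the point concerns who is counted and not a wrong number.

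**2. Replacement against the cap.** Let r be the proportion of randomised participants who are replaced. The protocol gives no value; 1% to 3% is an assumption.

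- If replaced people do not count towards 1708, the number randomised is 1708 / (1 − r): 1726, 1743 or 1761 for r = 1%, 2% or 3%. Each exceeds the maximum in section 4.1.
- If they do count, nobody can be recruited in their place once 1708 is reached, and the replacement rule does nothing.

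**3. Replacement against intention to treat.** Two cases need separating.

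- The participant agrees to data being kept. Section 10.2 can be met if this person stays in the denominator, but section 5.6 does not say so.
- The participant does not agree. Nothing need be kept, so the person cannot be analysed as section 10.2 requires. The opening of section 5.6 would have kept the data collected so far. This conflict is definite.

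**4. Is replacement needed for power?** Both calculations use the stated boundaries with futility followed and pooled variance. The percentages are assumptions.

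| Assumed % | Outcome data lost beyond the 3% allowance: evaluable N | Power | All kept, this % of the dexamethasone arm untreated: reduction | Power |
|---|---|---|---|---|
| 1 | 1708 × 0.96 = 1639.7 | 0.8965 | 0.08 × 0.99 = 0.0792 | 0.8933 |
| 2 | 1708 × 0.95 = 1622.6 | 0.8934 | 0.08 × 0.98 = 0.0784 | 0.8871 |
| 3 | 1708 × 0.94 = 1605.5 | 0.8903 | 0.08 × 0.97 = 0.0776 | 0.8806 |

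Every value lies within 2 points of 90%.

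**5. When would replacement bias the comparison?** Suppose there is no treatment effect and the people replaced are left out of the analysis. If k of 854 in one arm leave, with mortality q, and are replaced by people with mortality 0.40, that arm's mortality becomes 0.40 − k(q − 0.40)/854. The shift is zero if q = 0.40, and it cancels if k and q are the same in both arms. The documents give neither k nor q, so no size can be stated.

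**The case against.** The strongest defence is that section 5.6 is a recruitment rule and section 10.2 sets the analysis population. Recruiting one more person is compatible with intention to treat if the person who left stays in the denominator. This stands in part. A reader might infer that replaced participants are excluded from the primary analysis, but no sentence says so. What remains is an unreconciled text, a definite conflict for those who refuse data retention, and the cap.

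Second, the rule is narrow. It covers only withdrawal before any study-related procedure. Table 3 lists consent, medical history, demographics and baseline data among the study procedures at Day 0, and on that reading almost no randomised participant qualifies. Other withdrawals fall under the options in section 5.6, two of which keep data linkage and one of which keeps data already collected. This stands, and it is why the effect is probably small.

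Three stronger readings are tempting, and the documents do not support them.

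- *The window for replacement is longer in the usual-care arm, because only dexamethasone patients have an early dose.* Table 3 gives both arms ventilation, organ-support and adverse-event recording from Day 1. Section 7.2 records daily ICU data for all patients, section 7.5 takes the baseline blood sample in both arms, and section 11.2 records adverse events from consent.
- *Withdrawal by the site investigator is part of the same fault.* Section 5.6 says "The site PI can also withdraw a participant, based on clinical reasons", but it ties this neither to replacement nor to exclusion from analysis, and it requires the reasons to be documented.
- *The primary result will be biased by a calculable amount.* That needs a withdrawal rate, an imbalance between arms and a link to prognosis, none of which the protocol gives.

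Finally, the outcome of someone who refuses all data use cannot be recovered by any rule. That is true, but the person can still be counted as randomised with a missing outcome.

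**Conclusion.** The point holds in a limited form. The replacement provision in section 5.6 is not reconciled with section 10.2, section 4.1 or the retention sentence in its own opening paragraph. Because allocation is already known, it leaves room for selective loss by arm. Exclusion from the primary analysis is a possible reading and not a stated rule.

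The number of participants affected is probably small, and no bias is demonstrated: it is zero if these withdrawals are balanced between arms or unrelated to prognosis. Replacement also serves no sample-size purpose, since 1708 already carries 3% for loss. Without it, power falls no lower than 0.8806 in the scenarios examined, which rest on assumed rates of 1% to 3%. The provision therefore puts the randomised comparison at some risk for no gain, which is reason enough to remove it.

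**What to change.** - Delete the replacement sentence in section 5.6. The unexplained term for study-related procedures then no longer decides who is replaced.
- State that every randomised participant counts towards 1708 and stays in the intention-to-treat set, with 60-day vital status sought, including by linkage, as far as consent allows.
- Reconcile the two retention sentences in section 5.6, so that it is clear whether data up to withdrawal are kept always or only with agreement.
- Where all outcome data are refused, treat 60-day status as missing under the method that section 10.2 leaves to the SAP. Do not carry forward status at withdrawal: someone who leaves within hours would be counted as alive for a binary 60-day outcome.
- Report withdrawals before any study procedure by arm.

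The cost is a short wording amendment. It needs no extra patients and no change to the stopping boundaries.
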